The overall objectives of this study are to investigate the maintenance of weight loss, body composition and immunometabolic health outcomes over 52 weeks with liraglutide treatment, physical exercise, and the combination in individuals with obesity after a very low-calorie diet.

The hypothesis hierarchy was not clearly specified in the protocol and we hereby define it as described below.

Hypothesis hierarchy for the primary outcome:

1. We hypothesize that the combined treatment (exercise+liraglutide) is superior to placebo for maintaining total body weight loss. Superiority is claimed if the estimated difference between the changes in total body weight for the two groups (delta for exercise+liraglutide from V1 to V3 – delta for placebo from V1 to V3) favors the exercise+liraglutide group (difference in change \leq -4kg) and ~~that the lower limit of~~ the CI95% for the estimated difference does not exceed/include 0.
2. We hypothesize that liraglutide is superior to placebo for maintaining total body weight loss. Superiority is claimed if the estimated difference between the changes in total body weight for the two groups (delta for liraglutide from V1 to V3 – delta for placebo from V1 to V3) favors the liraglutide group (difference in change \leq -4kg) and ~~that the lower limit of~~ the CI95% for the estimated difference does not exceed/include 0.
3. We hypothesize that the combined treatment (exercise+liraglutide) is non-inferior to liraglutide for maintaining total body weight loss. Non-inferiority is claimed if the upper limit of the CI95% for the estimated difference between the changes in total body weight for the two groups (delta for exercise+liraglutide from V1 to V3 – delta for liraglutide from V1 to V3) is $<$ +4kg.
4. We hypothesize that exercise is non-inferior to placebo for maintaining total body weight loss. Non-inferiority is claimed if the upper limit of the CI95% for the estimated difference between the changes in total body weight for the two groups (delta for exercise from V1 to V3 – delta for placebo from V1 to V3) is $<$ +4kg.

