5. We hypothesize that the combined treatment (exercise+liraglutide) is superior to exercise for maintaining total body weight loss. Superiority is claimed if the estimated difference between the changes in total body weight for the two groups (delta for exercise+liraglutide from V1 to V3 – delta for exercise from V1 to V3) favors the exercise+liraglutide group (difference in change \leq -4kg) and the CI95% for the estimated difference does not include 0.

Secondary outcome:

6. We hypothesize that the combined treatment (liraglutide+exercise) is superior to liraglutide for body composition (total body fat percentage). Superiority is claimed if the estimated difference between the changes in total body fat percentage for the two groups (delta for liraglutide+exercise from V1 to V3 – delta for liraglutide from V1 to V3) favors the liraglutide+exercise group (difference in change \leq -1.5%) and ~~that the lower limit of~~ the CI95% for the estimated difference exceeds/does not include 0.

7. We hypothesize that exercise is superior to placebo for body composition (total body fat percentage). Superiority is claimed if the estimated difference between the changes in total body fat percentage for the two groups (delta for exercise from V1 to V3 – delta for placebo from V1 to V3) favors the exercise group (diffence in change $\leq -1.5\%$) and ~~that the lower limit of~~ the CI95% for the estimated difference ~~exceeds~~ does not include 0.
8. We hypothesize that the combined treatment (exercise+liraglutide) is non-inferior to exercise for body composition (total body fat percentage). Non-inferiority is claimed if the upper limit of the CI95% for the estimated difference between the changes in total body weight for the two groups (delta for exercise from V1 to V3 – delta for placebo from V1 to V3) is $< +1.5\%$.

Section 3: Study Methods

9 Trial design (from published protocol(1))

The S-LiTE trial (acronym for ‘Synergy effect of the appetite hormone GLP-1 (LiragluTide) and Exercise on maintenance of weight loss and health after a low calorie diet’) is an investigator-initiated, randomized, placebo-controlled, parallel group trial. The trial is triple-blinded with regards to study medication but not exercise intervention. The trial is registered at the European Clinical Trials Database (EudraCT Nr.: 2015-005585-32).

Description of Interventions

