Sample size for secondary endpoint body composition was calculated in relation to total body fat percentage. Based on previous exercise trials (20,50–52) the response within each treatment group was estimated to have a standard deviation of 2.1%. Thus, with 32 participants completing each study arm we will be able to detect a difference in delta body fat percentage of 1.5% between groups with a power of 0.8, assuming a two-sided α -level of 0.05. We will need 36 completers to attain a statistical power of 0.85. Sample size calculation for fat percentage was performed in relation to writing the SAP; after the intervention was started but prior to the termination of the intervention.

12 Framework

See point 8.

13 Statistical interim analyses and stopping guidance

No interim analyses were planned and no guidelines for terminating the trial early was made.

14 Timing of final analyses

Results from V1 to V3 will be analyzed when the final participant completes the trial. Analyses including V4 will be performed when the final participant has completed V4.

15 Timing of outcome assessments

Body weight is measured at week -8 (V0), -7, -6, -5, -4, -3, -2, -1, 0 (V1), 1, 2, 4, 9, 13, 17, 22, 26, 39, 46, 52 (V3) and 104 (V4).

Body composition is measured at V0, V1, V3 and V4.

See point 26 for timing of descriptive/explorative outcome assessments.

Section 4: Statistical Principles

16-18 Confidence intervals and P values

P-values and 95% confidence intervals will be presented for comparisons (between and within group) and will not be adjusted for multiplicity. 95% confidence intervals will be presented for estimated levels and will not be adjusted for multiplicity. A hierarchical testing procedure will be used to control the type 1 error for tests with predefined hypotheses (see point 8); all subsequent tests will be regarded as descriptive/explorative if a test fails to confirm a given hypothesis. All non-hypothesis-based tests are per definition of a descriptive/exploratory nature. Statistical significance will be claimed if the null hypothesis is rejected at the alpha level of 0.05 (two-sided), i.e. the P-value of the null hypothesis test is ≤ 0.05 . 95% confidence intervals will be required to support the tested hypothesis for hypothesis-based tests (see 8), and for exploratory/descriptive test on an absolute or relative scale not include 0 or 1 respectively.

19-20 Adherence and protocol deviations and Analysis populations

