Secondary outcome: Secondary outcome body composition is defined as change in total body fat percentage (measured to the nearest 0.01 % in fasted state with dual-energy X-ray absorptiometry (DXA) scans) from V1 to V3. In most exercise interventions with aerobic exercise, almost exclusively fat mass is lost whereas lean mass is close to unchanged (19–22). In weight loss studies with liraglutide, a combination of fat and lean mass is lost (31,32). The clinically relevant effect size for changes in fat percentage is not well described or investigated. However, based on the results of previous exercise interventions (20,57), a decrease in fat percentage equivalent of approximately 1.5 % seems to be physiologically relevant.

Descriptive/explorative outcomes:

Change from V1 to V3:

- Body composition (fat free mass (kg) and fat mass (kg))
- Circulating biomarkers of metabolic regulation to evaluate metabolic health (fasting and 3h AUC glucose (mmol/L and mmol/L*min) and fasting and 3h AUC insulin (pmol/L and pmol/L*min) for HOMA-IR and Matsuda index, HbA1c (mmol/mol), waist circumference (cm), systolic and diastolic blood pressure (mmHg), lipids (total cholesterol, HDL, LDL, and triglycerides (mmol/L))
- Safety (adverse events). Adverse events with an incident of $\geq 5\%$ in any treatment group and all serious adverse events will be reported by system organ class and preferred term for participants in all four treatment groups separately and for liraglutide pooled (exercise and non-exercise) and placebo pooled (exercise and non-exercise). Events will be reported as percentage of individuals experiencing an adverse event.
- Self-rated quality of life will be measured with the SF-36 questionnaire. Eight health concepts ranging from 0-100 will be scored: physical functioning, role limitations due to physical health problems, role limitations due to personal or emotional problems, energy/fatigue, emotional well-being, social functioning, pain, and general health perception.
- Peak oxygen uptake (absolute (ml/min) and relative (ml/min/kg))
- Stair test (S) and maximal isometric strength test (N)
- Use of medication (n, frequency)
- Meal related appetite response
- Determination of daily physical activity and sleep
- Systemic markers of immune-metabolism and oxidation
- Endothelial function
- Immuno-metabolic changes in the subcutaneous adipose tissue
- Gene expression profile of circulating inflammatory cells
- Bone health

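### Hypothesis 8 claims non-inferiority of the combination to exercise on body fat percentage, but its decision rule tests exercise minus placebo on body weight

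*SAP*

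**What the plan says.** Hypothesis 8, the last in the SAP section 8 hierarchy and listed under the secondary outcome, is that "the combined treatment (exercise+liraglutide) is non-inferior to exercise for body composition (total body fat percentage"). The next sentence gives the criterion: the upper limit of the 95% interval for the difference between "changes in total body weight for the two groups (delta for exercise from V1 to V3 – delta for placebo from V1 to V3") must be below +1.5%.

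The related passages are:

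- Section 8, hypothesis 4: "We hypothesize that exercise is non-inferior to placebo for maintaining total body weight loss". Its rule uses exercise minus placebo on body weight, with a margin of +4 kg.
- Section 8, hypothesis 7: "We hypothesize that exercise is superior to placebo for body composition (total body fat percentage"). It needs an exercise-minus-placebo estimate of -1.5% or lower and a 95% interval that excludes 0.
- Section 26: "Secondary outcome body composition is defined as change in total body fat percentage" from V1 to V3, measured by DXA.
- Section 12 only points back to section 8. Sections 16-18 require the intervals to support the hypotheses as set out there, and make every later test exploratory once one fails.
- The list of changes from version 1 to 2 covers the superiority wording and the added minimally important differences. It does not mention this rule.

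**The concern.** A confirmatory claim is only as good as the rule that decides it. This rule contains neither the arm the claim is about (exercise+liraglutide) nor the outcome it is about (fat percentage). Hypothesis 8 is also the only confirmatory comparison of the combination with exercise on fat percentage, since hypothesis 6 compares the combination with liraglutide and hypothesis 7 compares exercise with placebo. If the rule is followed, the trial can report non-inferiority on that comparison without having tested it. If the rule is changed silently once results are known, the claim can no longer be shown to have been pre-specified. Section 27 gives the analysis to a researcher who took no part in running the trial and who will therefore depend on the written rule.

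**Working it through.** **1. Stated hypothesis and written rule side by side**

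| Element | Hypothesis 8 as stated | Rule as written | Where the written element fits |
|---|---|---|---|
| Outcome | total body fat percentage | total body weight | hypothesis 4 |
| Contrast | exercise+liraglutide minus exercise | exercise minus placebo | hypotheses 4 and 7 |
| Margin | fat-percentage threshold | +1.5% | fat percentage (weight margins are 4 kg) |

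In hypotheses 1 to 7 the bracketed contrast and the outcome match the stated hypothesis. Hypothesis 8 is the only exception.

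**2. Inputs**

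Fat percentage (section 11): "the response within each treatment group was estimated to have a standard deviation of 2.1"%, and "with 32 participants completing each study arm we will be able to detect a difference in delta body fat percentage of 1.5% between groups" with power 0.8 at two-sided 0.05. Weight (section 11): SD 5.5 kg, 30 completers per arm. The calculations assume normality, equal SDs, independent arms and completers only.

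**3. The plan's own sample size**

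n per arm = 2(z₀.₉₇₅ + z_power)² × SD²/difference².

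- Power 0.80: 2 × (1.960 + 0.842)² × 2.1²/1.5² = 30.8, so 31.
- Power 0.85: 2 × (1.960 + 1.036)² × 2.1²/1.5² = 35.2, so 36.

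With the t distribution, power is 0.803 at 32 per arm and 0.848 at 36. The stated 32 and 36 are reproduced.

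**4. Written arms, read on fat percentage**

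Hypothesis 8 is confirmatory only after hypothesis 7 has passed. Hypothesis 7 requires an estimate of -1.5 or lower with an interval excluding 0, so the upper limit U of exercise minus placebo satisfies U < 0. Since 0 < 1.5, U < +1.5 follows. The probability of passing hypothesis 8 given hypothesis 7 is exactly 1, whatever the sample size.

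Example: exercise is truly 1.5 points better than placebo, and the combination is truly 1.5 points worse than exercise, which is the edge of non-inferiority. SE = 2.1 × √(2/32) = 0.525. In 400,000 simulated trials:

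- hypothesis 7 passed in 49.9%;
- the written arms passed hypothesis 8 in 100% of those;
- the contrast hypothesis 8 names passed in 2.5% of all trials, and in 0.4% of those passing hypothesis 7.

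**5. Rule read literally, on weight**

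The margin has the wrong unit. Taking 1.5 as kg (an assumption), P(pass) = Φ((1.5 − d)/SE − 1.96), with SE = 5.5 × √(2/30) = 1.420 and d the true exercise-minus-placebo difference:

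- d = 0 kg: Φ(−0.904) = 0.18
- d = −2 kg: Φ(0.505) = 0.69
- d = −4 kg: Φ(1.913) = 0.97

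The combination arm does not enter. Taking 1.5% as a share of body weight, with the heights of 170-174 cm and BMI range of 32-43 in section 26, weight is 32 × 1.70² = 92.5 kg to 43 × 1.74² = 130.2 kg. The margin would then be about 1.4 to 2.0 kg, which the plan nowhere defines.

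**6. The contrast hypothesis 8 names**

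With margin 1.5, SD 2.1 and true difference 0, the formula in step 3 again gives 31 per arm for power 0.80 and 36 for 0.85. At 32 per arm, power = Φ(1.5/0.525 − 1.96) = Φ(0.897) = 0.815, and the error at the margin is Φ(−1.96) = 0.025.

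**The case against.** The strongest reply is that the intended test can be recovered. The first sentence of hypothesis 8 names the arms and the outcome, section 26 defines the secondary outcome only as fat percentage, and the +1.5% margin belongs to fat percentage. An exercise-minus-placebo interval cannot support a hypothesis about the combination, so sections 16-18 arguably expose a conflict rather than bind the analyst to the wrong contrast. A rule that cannot be applied literally may prompt a query instead of a false claim. All of this supports the proposed correction, but none of it supplies a valid written rule.

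A second reply is that the 100% mixes a corrected outcome with uncorrected arms and conditions on hypothesis 7 alone, whereas hypotheses 1, 3, 5 and 6 constrain the combination arm first. This stands as a limit on the harm. Suppose liraglutide equals placebo on fat percentage and the combination is 1.5 points worse than exercise. With a true exercise benefit e over placebo, hypotheses 6 and 7 use separate arms and pass together with probability Φ((e − 3)/0.525) × Φ((e − 1.5)/0.525). At 32 per arm the estimate threshold of -1.5 is the stricter condition, because −1.5 + 1.96 × 0.525 = −0.47 is already below 0.

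- e = 1.5: 0.002 × 0.50, about 0.1%
- e = 2: about 2.4%
- e = 2.5: about 17%
- e = 3: about 50%

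These figures are before hypotheses 1 to 5 are applied. The overall risk of a false claim therefore runs from negligible to large, depending on the exercise effect. The earlier hypotheses do not test the combination against exercise on fat percentage, so on this reading the hypothesis 8 step itself still adds no test.

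Finally, hypothesis 8 is last in the order and concerns a secondary outcome, so no other confirmatory test is damaged. That is correct and limits the scope.

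**Conclusion.** The concern holds. The decision rule for hypothesis 8 is wrong as written in both outcome and contrast, and no other part of the SAP repairs it. On the fat-percentage reading of the written arms, hypothesis 8 passes with certainty once hypothesis 7 has passed; this is a matter of logic and rests on no distributional assumption. On the literal reading, a weight difference in kg is set against a percentage margin and the result has no meaning. The simulated and tabulated probabilities rest on the SDs and completer numbers in section 11, and the weight figures also on reading 1.5 as kg. That the text was carried over from hypothesis 4 or 7 is likely but cannot be shown. The damage is confined to hypothesis 8. Because the faulty sentence decides a confirmatory claim, it must be corrected.

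**What to change.** Rewrite the second sentence of hypothesis 8 in section 8 so that:

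- the outcome is the change in total body fat percentage from V1 to V3;
- the contrast is the change with exercise+liraglutide minus the change with exercise;
- non-inferiority is claimed if the upper 95% limit of that contrast is below +1.5%, stated as percentage points of body fat.

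Record the correction as a dated entry in the SAP revision list, made before group allocation is unblinded. If unblinding has already taken place, report the written rule, the corrected rule and the date of the change alongside the result.

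The cost is one sentence and one revision entry. The design, data collection, mixed model and sample size do not change: power for the corrected test is about 0.8 at 32 completers per arm if the true difference is 0.

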Statistical Analysis Plan for clinical outcomes in the S-LiTE study

Section 1: Administrative information

Title: **Synergy effect of the appetite hormone GLP-1 (*LiragluTide*) and *Exercise* on maintenance of weight loss and health after a low calorie diet – the *S-LiTE* randomized trial**

Publication date: ~~427 March~~ [November 2020](#)~~19~~

SAP version: ~~2~~~~1~~

Protocol version: 10

The Universal Trial Number (UTN): U1111-1173-3104

EudraCT no: 2015-005585-32

ClinicalTrials.gov Identifier: NCT04122716

This document is a supplement to the S-LiTE study protocol (1) and contains the statistical analysis plan for the article with the tentative title “A randomized controlled trial of the combined effects of the GLP-1 receptor agonist liraglutide and exercise on maintenance of weight loss, body composition and health after a very low-calorie diet” This document follows the guidelines for content of statistical analysis plans in clinical trials (2).

Scientific board

[name], [name]

[name], Professor, DMSci

[name], Professor, DMSci

[name], Professor, DMSci

[name] [name], PhD Student

[name], MSC, PhD student

[name] [name], PhD student

[name] [name]

Statistical advisor

[name] [name], postdoc

Sponsor-Investigator

[name], [name]

University of Copenhagen

Faculty of Health Sciences

Department of Biomedical Sciences

[name]

[name]

Denmark

[contact]/ [name]

[contact]

SAP revisions

Changes from version 1 to 2

1. Item 8 (Page 6-7): The minimally important differences (physiologically relevant changes) for the primary and secondary outcomes (which was defined in item 26) have now also been added to the hypotheses for clarity. In the hypotheses section of SAP version 1 it was stated that superiority would be claimed if the changes to an outcome favored the given group (see individual hypotheses on page 6-7) and the lower limit of the CI95% for the estimated difference did not *exceed* 0. The latter part has been corrected to “does not *include* 0” to reflect that a reduction is favorable as stated in the hypothesis.

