Identical test days will take place before the initial weight loss phase (V0, week -8), after initial weight loss (V1, week 0) and after 52 weeks of treatment (V3). For details on test days, see study protocol (1).

Weight consultations will be performed weekly during initial VLCD phase and at week 1, 2, 3, 4, 9, 13, 17, 22, 26, 32, 39 and 46. Fasting blood samples will be collected at week 4, 13, 26 and 39.

Finally, participants will be invited to complete a post-trial unsupervised follow-up visit (V4) 1 year after intervention completion.

10 Randomization

After the initial eight-week VLCD phase, participants will be randomized after the test day (V1) to one of the four study groups in a 1:1:1:1 ratio in accordance with a subject randomization list (SRL) provided by Novo Nordisk. An un-blinded study nurse (not otherwise associated with the trial) will allocate study participants according to the SRL. Randomization will be stratified by sex (male/female) and age (below/above 40 years).

11 Sample size

Sample size calculation for total body weight:

Sample size for primary endpoint was calculated in relation to total body weight. Based on previous weight loss studies with liraglutide (15,49), we estimate the response within each treatment group to be normally distributed with a standard deviation of 5.5 kg. Thus, with 30 participants completing each study arm we will be able to detect a difference in delta of 4 kg between groups with a power of 0.8, assuming a two-sided α -level of 0.05. We will need 34 completers in each arm in order to attain a statistical power of 0.85 and 40 completers in each arm to attain a statistical power of 0.90. In our previous study, 10 % of participants who entered the initial VLCD phase did not complete this phase (15). With 222 recruited study participants and an expected dropout rate of 25 % after randomization, we expect to have at least 30 participants from each study arm to complete the trial.

Sample size for total body fat percentage

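### Section 11's power is for rejecting zero difference, but Section 8 also requires the estimate to reach -4 kg or -1.5%; at a true difference of that size, power for the claim is 0.50

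*SAP*

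**What the plan says.** **Section 11 (Sample size).** For weight, with an SD of 5.5 kg, two-sided alpha 0.05 and 30 completers per arm, "we will be able to detect a difference in delta of 4 kg between groups with a power of 0.8". It adds that 34 completers per arm give 0.85, and that the trial needs "40 completers in each arm to attain a statistical power of 0.90". For body fat, with an SD of 2.1% and 32 completers per arm, "we will be able to detect a difference in delta body fat percentage of 1.5% between groups with a power of 0.8"; 36 give 0.85.

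**Section 8 (Objectives).** The superiority criterion has two parts. Hypothesis 5 shows it most cleanly: superiority is claimed if the estimate "favors the exercise+liraglutide group (difference in change \leq -4kg) and the CI95% for the estimated difference does not include 0". Hypotheses 1 and 2 use the same rule, and hypotheses 6 and 7 use it with -1.5% body fat. Hypotheses 3, 4 and 8 are non-inferiority hypotheses and are not affected.

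**Sections 16-18 (Confidence intervals and P values).** On the testing hierarchy: "all subsequent tests will be regarded as descriptive/explorative if a test fails to confirm a given hypothesis". Significance is defined there as P at or below 0.05, two-sided, with no mention of the threshold. For the predefined hypotheses the text refers back to Section 8 but names only the confidence interval as required support.

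**SAP revisions.** The list of changes to version 2 says that the minimally important differences, already defined in item 26, "have now also been added to the hypotheses for clarity". It lists no change to Section 11.

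**The concern.** The same 4 kg and 1.5% appear as the difference to be detected in Section 11 and as the value the estimate must reach in Section 8. Power to reject zero at a true 4 kg is not the probability of observing at least 4 kg. Section 11 is the SAP's only statement of power, so a reader would naturally take it as the chance of a superiority claim at the minimal important difference.

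The hierarchy is also affected. Suppose hypothesis 1 gives an estimate of -3.5 kg with an interval that excludes zero. Sections 16-18 would call this statistically significant, while Section 8 would not allow a superiority claim. Read literally, the two sections together mean that hypothesis 1 is not confirmed and every later test becomes exploratory. Sections 16-18 do not say so outright.

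**Working it through.** **Inputs, all from the SAP.** SD 5.5 kg with 30, 34 or 40 completers per arm; SD 2.1% with 32 or 36; two-sided alpha 0.05; equal allocation (Sections 10, 11 and 16-18). Thresholds of 4 kg and 1.5% (Section 8). True effects other than 4 kg and 1.5% are assumptions, because the SAP states no expected effect for this trial. Differences are written below as positive sizes of benefit.

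**Step 1: reproduce Section 11.** The standard error is SE = SD × √(2/n).

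- Weight: 5.5 × √(2/30) = 1.420 kg; 1.334 kg at n = 34; 1.230 kg at n = 40.
- Fat: 2.1 × √(2/32) = 0.525%; 0.495% at n = 36.

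Power to reject zero, Φ(difference/SE − 1.96), is 0.804, 0.851 and 0.902 for weight and 0.815 and 0.858 for fat. With the noncentral t it is 0.791, 0.840 and 0.895, and 0.803 and 0.848. Section 11 is therefore correct as power against zero.

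**Step 2: which part of the Section 8 rule binds?** The smallest significant estimate is t × SE:

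- Weight: 2.84, 2.66 and 2.45 kg (n = 30, 34, 40).
- Fat: 1.05% and 0.99% (n = 32, 36).

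All lie below the thresholds, so at the planning SDs an estimate that reaches the threshold is almost always significant as well.

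**Step 3: power for the superiority claim.** With the threshold binding, power ≈ Φ((true difference − threshold)/SE). At a true 4 kg or 1.5% this is Φ(0) = 0.50, whatever n is. At a true 5 kg and n = 30 it is Φ(1/1.420) = 0.76. The values for the Section 8 rule below were simulated with an estimated variance and t intervals (2,000,000 runs each).

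| True difference | n per arm | Section 8 rule | CI alone |
|---|---|---|---|
| 3 kg | 30 / 40 | 0.24 / 0.21 | 0.55 / 0.67 |
| 4 kg | 30 / 34 / 40 | 0.50 / 0.50 / 0.50 | 0.79 / 0.84 / 0.90 |
| 4.5 kg | 30 / 40 | 0.64 / 0.66 | 0.88 / 0.95 |
| 5 kg | 30 / 40 | 0.76 / 0.79 | 0.93 / 0.98 |
| 6 kg | 30 / 40 | 0.92 / 0.95 | 0.99 / 1.00 |
| 1.5% | 32 / 36 | 0.50 / 0.50 | 0.80 / 0.85 |
| 2.0% | 32 / 36 | 0.83 / 0.84 | 0.96 / 0.98 |

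**Step 4: true difference needed for 80% power.** This is threshold + 0.842 × SE.

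- Weight: 4 + 0.842 × 1.420 = 5.2 kg (n = 30); 5.1 kg (n = 34); 5.0 kg (n = 40).
- Fat: 1.5 + 0.842 × 0.525 = 1.94% (n = 32); 1.92% (n = 36).

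**Step 5: sensitivity to the SD.** Over an assumed SD range of 5.0 to 6.5 kg, 80% power needs 5.1 to 5.4 kg at n = 30 and 4.9 to 5.2 kg at n = 40. The interval becomes the harder condition only when the observed SD exceeds threshold/(t × √(2/n)): 7.7, 8.3 and 9.0 kg for n = 30, 34 and 40, and 3.0% and 3.2% for n = 32 and 36. Power at a true 4 kg then falls below 0.50 (0.43 at SD 8.5 kg, n = 30).

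**The case against.** **The threshold may be only a remark on relevance.** It stands in parentheses after the word for favouring a group, the revision list says it was added for clarity, and Sections 16-18 name only the P value and the interval. On that reading Section 11's power stands. The reading is possible but less literal: the inequality sits inside the sentence that sets the condition for claiming superiority, joined to the interval condition by *and*. If a remark was meant, Section 8 would have to say so.

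**Sections 16-18 do not strictly contradict Section 8.** Statistical significance and a superiority claim may have different conditions, and Sections 16-18 refer back to Section 8. This stands in part. The fault is an unstated link, not an outright conflict, and one sentence closes it.

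**The boundary case is the least informative one.** Item 26 defines 4 kg as a minimal important difference, not an expected effect. Section 7 cites a 5.4% weight loss against placebo with liraglutide in people without diabetes. Taking 4 kg as 4%, the middle of item 26's 3-5%, implies 4/0.04 = 100 kg, so 5.4% would be about 5.4 kg. Power under the Section 8 rule is then about 0.84 (n = 30) to 0.87 (n = 40), against 0.96 to 0.99 for the interval alone. That is a fair mitigation for hypotheses 1 and 2. It is not a planning effect in the SAP, though, and it comes from a setting without the preceding diet phase. Section 11 itself chose to state power at the boundary.

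**Log-transformation.** Section 27 allows it, with results given as ratios, to which a threshold in kg does not directly apply. This is true, but the Section 8 rule is written in kg.

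**The timing limits the benefit.** The SAP was written after the intervention had started, so restated power cannot change the sample size. That is so; the correction serves interpretation and reporting.

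**Conclusion.** The concern holds. Section 11's arithmetic is correct for rejecting zero but does not describe the claim defined in Section 8. At a true 4 kg or 1.5%, power for a superiority claim is 0.50 per test instead of the stated 0.80 to 0.90 (weight) or 0.80 to 0.85 (fat), and going from 30 to 40 completers does not raise it. The shortfall shrinks as the true effect grows and is small by 6 kg.

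The 0.50 is a ceiling that needs only an estimator distributed symmetrically around the true value; it does not depend on the SD, the sample size or the choice of the Section 27 mixed model. The 5.0 to 5.2 kg and 1.92 to 1.94% figures do depend on the planning SDs and on a two-sample comparison of completers. The rule is stricter than the interval alone and adds no type I error. What is at stake is an overstated chance of success near the minimal important difference, and some doubt about when the hierarchy stops. This should be fixed.

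**What to change.** 1. In Section 11, label the existing figures as power to reject zero difference, and add:

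> Under the superiority rule of Section 8 and the same planning assumptions (two-sample comparison of completers, SD 5.5 kg or 2.1%), power is 0.50 when the true difference equals 4 kg or 1.5%. Power of 80% needs a true difference of about 5.2 kg (30 completers per arm), 5.1 kg (34), 5.0 kg (40), 1.94% (32) or 1.92% (36).

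2. In Sections 16-18, add:

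> A hypothesis is confirmed only if its full criterion in Section 8 is met, including the threshold for superiority hypotheses; P ≤ 0.05 alone does not confirm it.

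Sections 8, 11 and 16-18 then rest on one criterion. The cost is SAP wording only: no patients, no data and no change to the model. The second sentence writes out the literal reading of Sections 8 and 16-18, so the decision rule as written does not change. The restated power is less favourable to the sponsor.

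### The body-fat power of 0.80–0.85 in SAP section 11 is for one free-standing, CI-only test; the hierarchy and the success rule in section 8 do not deliver it for a confirmatory H6

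*SAP*

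**What the plan says.** Section 11 bases the body-fat calculation on one planning SD: "the response within each treatment group was estimated to have a standard deviation of 2.1" percentage points. It states that "with 32 participants completing each study arm we will be able to detect a difference in delta body fat percentage of 1.5" points at power 0.80 and two-sided alpha 0.05, and then: "We will need 36 completers to attain a statistical power of 0.85". For weight, "we estimate the response within each treatment group to be normally distributed with a standard deviation of 5.5 kg", and "with 30 participants completing each study arm we will be able to detect a difference in delta of 4 kg between groups" at power 0.80.

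Section 8 numbers eight hypotheses in one run: H1 to H5 on weight, H6 to H8 on body fat. H1, H2 and H5 are superiority tests on weight. Each needs an estimated difference of -4 kg or lower and a 95% CI that excludes 0. H3 and H4 are non-inferiority tests with a +4 kg margin. H6 and H7 need an estimate of -1.5 points or lower and a CI that excludes 0.

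Sections 16-18 apply a hierarchical procedure to the predefined hypotheses of section 8: "all subsequent tests will be regarded as descriptive/explorative if a test fails to confirm a given hypothesis". Section 11 does not say how its power figures relate to that procedure or to the estimate thresholds.

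**The concern.** A reader of section 11 will take 0.80 to 0.85 as the chance that the trial confirms a body-fat benefit if the planning assumptions are true. That chance differs from the stated figure for two reasons.

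- **The sequence.** H6 is sixth in line. One missed weight test among H1 to H5 makes it exploratory, whatever the body-fat data show.
- **The success rule.** The power formula counts a success whenever the CI excludes 0. Section 8 also sets a minimum estimate, and that minimum equals the difference used for planning.

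At stake is how well the secondary outcome is said to be powered. An exploratory H6 could be taken as bad luck in an 80%-powered test when it was the likelier result under some of the plan's own planning values.

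**Working it through.** **1. The plan's own figures.** SE of a difference = SD × √(2/n).
- Fat, n = 32: 2.1 × √(2/32) = 0.525; 1.5/0.525 = 2.857; power ≈ Φ(2.857 − 1.960) = 0.815, or 0.803 by the noncentral t.
- Fat, n = 36: 2.1 × √(2/36) = 0.495; 1.5/0.495 = 3.03; power ≈ 0.858, or 0.848 by the noncentral t.
- Weight, n = 30: 5.5 × √(2/30) = 1.420; 4/1.420 = 2.817; power ≈ 0.804, or 0.791 by the noncentral t.

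Section 11 reproduces for a single CI-based test.

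**2. What the estimate threshold does.** At n = 32 the CI half-width is about 1.98 × 0.525 = 1.04 points for fat and 1.98 × 1.375 = 2.72 kg for weight. An estimate at the threshold (-1.5 points or -4 kg) already has a CI that excludes 0, so the threshold decides the result. When the true difference equals the threshold, the estimate falls on the required side half the time. H6 alone therefore has a chance of 0.50 under the full rule, at 32, 36 or any larger n.

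**3. The sequence.** I simulated four arm means with pooled-variance t intervals (400,000 draws per setting); shared arms induce the correlation between tests.
- From the SAP: SDs of 5.5 kg and 2.1 points, true H6 difference of 1.5 points, equal arms.
- Assumed, because the SAP gives none: the true weight effects in the four arms, and a within-person correlation of 0 to 0.6 between weight and fat change.

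Cumulative chance that all tests so far succeed, n = 32, liraglutide -4, combination -4, exercise 0 kg relative to placebo:

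| Rule | H1 | H1–H2 | H1–H3 | H1–H4 | H1–H5 | H1–H6 |
|---|---|---|---|---|---|---|
| CI only | 0.82 | 0.72 | 0.62 | 0.55 | 0.49 | 0.40–0.43 |
| Full section 8 rule | 0.50 | 0.33 | 0.30 | 0.28 | 0.18 | 0.09–0.11 |

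Hand check on the second row: H1 and H2 share the placebo arm, so their estimates correlate at 0.5, and both fall beyond their true means with probability 1/4 + arcsin(0.5)/(2π) = 1/3. With fat and weight uncorrelated, the last step is 0.18 × 0.50 = 0.09.

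**4. Range over assumptions.** Section 11's recruitment figures imply 222 × 0.90 × 0.75 / 4 = 37.5 completers per arm, so 37 is included.

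| Exercise / liraglutide / combination (kg) | n per arm | H6 confirmed, CI only | H6 confirmed, full rule |
|---|---|---|---|
| 0 / -4 / -4 | 32 | 0.40–0.43 | 0.09–0.11 |
| 0 / -4 / -4 | 36 | 0.50–0.53 | 0.10–0.11 |
| 0 / -4 / -4 | 37 | 0.52–0.55 | 0.10–0.11 |
| -2 / -4 / -6 | 32 | 0.54–0.55 | 0.12–0.13 |
| -2 / -6 / -8 | 32 | 0.78–0.79 | 0.43 |
| -2 / -6 / -8 | 37 | 0.85 | 0.44 |

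The simulation analyses completers with t intervals. The planned mixed model may shift these values a little.

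**The case against.** Section 11 contains no arithmetic error and never claims 0.80 for a gated test. Power per comparison is the usual way to report it, and sections 16-18 state openly what a failed test does. The fat calculation was made after the intervention had started, so it did not set the size of the trial. Type I error control is unaffected, and estimates, intervals and P-values are still reported if the sequence stops. All of this stands. The defect is an omission.

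Two points of wording could soften it. The heading that announces a hierarchy names only the primary outcome, and H6 to H8 stand under their own heading. But the numbering is continuous, and sections 16-18 cover every predefined hypothesis with no second starting point and no alpha split. The revision note also says that the thresholds were added for clarity, so someone might read them as description. As written they are part of the condition for claiming superiority. If they are only descriptive, the CI-only figures apply, and these too fall short of 0.80–0.85 unless the weight effects are clearly larger than 4 kg.

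A reader might go further in two ways that the SAP does not support.
- **One replacement figure, such as 0.4–0.55, as the plan's own.** The SAP gives no four-arm means. CI-only results run from 0.40 to about 0.85 over the means and sample sizes tried, and that figure ignores the thresholds.
- **Moving H3 and H4 behind the body-fat tests.** With liraglutide and combination at -5.4 kg and exercise at 0 (n = 32), this lifts H6 from 0.53–0.57 to 0.75–0.76 by the CI rule, but only from 0.26–0.30 to 0.33–0.35 under the full rule. It also puts primary-outcome tests behind secondary ones. That is a design preference and corrects no error.

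**Conclusion.** The point holds as an omission in section 11. Power of 0.80 (32 completers) and 0.85 (36) is correct for a single comparison judged by its CI alone, and a confirmatory H6 is not such a comparison. The direction is certain: passing five earlier tests and meeting an added threshold can only lower the chance. The size depends on assumed arm means. At 32 per arm it runs from about 0.40–0.43 (CI rule) and 0.09–0.11 (full rule) with liraglutide and combination at -4 kg and exercise at 0, to about 0.78–0.79 and 0.43 with liraglutide -6, exercise -2 and combination -8 kg. One result needs no assumption about weight: at the planned 1.5-point difference, H6 cannot exceed 0.50 under the full rule at any sample size.

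**What to change.** In section 11, label 0.80 and 0.85 as the power of a single comparison judged only by whether the CI excludes 0. Beside them, give the probability of reaching H6 and of confirming it under the hierarchy and the full success rule of section 8. State the assumed true weight effects in all four arms and the assumed correlation between weight and fat change, and show a range such as the one above. The order of the hypotheses need not change.

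The cost is a paragraph in the SAP and a less favourable stated figure. No analysis, sample size or data collection changes.
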